## **6.1 Screening, Randomization and Treatment (Visit 1; Day 1)**

Procedures as identified in Table 6-1:

- Informed consent
- Prior medications
- Medical history
- Urine pregnancy test (females of child-bearing potential only)
- Scabies assessment
- Vital signs (height at Visit 1 only)
- General skin assessment for eligibility
- Eye assessment
- Review eligibility criteria
- Randomization
- Weigh, dispense and instruct on IP application at home the same day\*
- Instruct on showering  $\geq 6$  hours post-treatment and at least 1 hour prior to Visit 2
- Instructions to prevent re-infestation
- Concomitant medications

\*Subjects less than 12 years of age should be assisted with administration by a parent, guardian or caregiver.

## **6.2 Follow-up Safety Assessment Visit (Visit 2, Day 2)**

- General skin and eye assessments for irritation and wash-off confirmation
- Collect and weigh used IP bottle
- Confirm compliance
- Instructions to prevent re-infestation
- Concomitant medications
- Adverse events

**6.3 AE Follow-up Visit (Day 3 + 6 days; conducted only if a subject reports an adverse event assessed as related by the PI on Day 2)**

- PI assessment of reported AE

**6.4 Phone Call (Day 14 +/- 2 days)**

- Instructions to prevent re-infestation
- Concomitant medications
- Adverse events

**6.5 AE Follow-up Visit (Day 14 + 7 days; conducted only if a subject reports an adverse event assessed as related by the PI on the Day 14 well-being phone call)**

- PI assessment of reported AE

**6.6 Final Visit (Visit 3/ET, Day 28 + 2 days)**

- Urine Pregnancy Test (females of child bearing potential)
- Efficacy assessments
- Vital signs
- General skin and eye assessments for irritation
- Review subject compliance
- Concomitant medications
- Adverse events
- If subjects are not completely cured at this visit (Day 28), those subjects will be provided 5% Permethrin as rescue medication.
- For those subjects with an ET visit, 5% Permethrin will not be dispensed and the PI will refer the subject to their primary care physician for follow-up.

**6.7 Early Termination Procedures**

The term "Early Termination" refers to a subject's non-completion of a study whether by his or her own choice or the investigator's decision or due to discontinuation of the study by ParaPRO LLC. In the absence of a medical contraindication or significant protocol violation, every effort will be made by the Investigator to keep the subject in the study. Should the subject decide to withdraw, an early termination visit should be conducted, which will include all procedures

normally done at Visit 3. The ET subject will not be dispensed 5% Permethrin and the PI will refer the subject to their primary care physician for follow-up.

The primary reason for a subject withdrawing prematurely should be selected from the following categories:

***Adverse Event or Serious Adverse Event***—events that are associated with discontinuation.

***Noncompliance with protocol***—the subject failed to adhere to the protocol requirements. The deviation necessitated premature termination from the study.

***Withdrawal of Consent***—subject desires to withdraw from further participation in the study in the absence of an adverse event or a medical need to withdraw.

***Lost to Follow-up***—the subject did not return for one or more follow-up visit(s) following dispensing of test drug. The reason was unknown and appropriate due diligence was exerted by the investigator to contact the subject and encourage their return.

***Other***—causes of premature termination from the study other than the above, such as theft or loss of IP, termination of study by ParaPRO LLC, etc. The details of the premature termination in this “other” category should be documented fully.

The investigator should notify Concentrics Research promptly when a subject is withdrawn, or if the study is stopped at his/her site by the IRB or if the investigator elects to stop the study.

## **6.8 Subject Completion Criteria**

Successful completion of the study by “index” subjects will occur at Day 28 (Visit 3) if the “index” subject is completely cured of scabies. Other household members will complete the study at Day 28 after safety assessments are completed.

## **6.9 Protocol Deviations**

This study is intended to be conducted as described in this protocol. Any changes/deviations to the protocol must be reported to the IRB (Schulman IRB Cincinnati, OH 45242). In the event of a significant deviation from the protocol due to an emergency, accident, or mistake, the investigator or designee must also notify the Medical Monitor within 24 hours from when the deviation was identified.

## **7 DETAILED DESCRIPTION OF ASSESSMENTS**

### **7.1 Informed Consent**

Written informed consent will be obtained from subjects who are 12 years of age and older as well as the parent or legal guardian of subjects who are 4-17 years of age before any study procedures are performed. In addition to the parent or legal guardian signing the informed consent, verbal and written assent will be obtained from subjects who are between the ages of 7-11 years of age. Assent is not required for subjects 4-6 years of age; however, the parent or legal guardian must sign consent. All potential subjects for the study (or their legal guardians) will be given a copy of the Institutional Review Board (IRB)-approved informed consent form to read. The IRB is Schulman IRB (Cincinnati, OH 45242).

The assent and/or consent forms will be discussed in detail with each potentially eligible subject and the parent or legal guardian of subjects 4-17 years of age, if applicable. The PI or qualified designee will explain all aspects of the study in lay language and answer all the subject's questions regarding the study. The PI or designee will inform the subject as to the nature, aims, duration, potential hazards, and procedures to be performed during the study and that his or her medical records may be reviewed. The PI or designee will also explain that the subject is completely free to refuse to enter the study or to withdraw from it at any time. Subjects who refuse to participate or who withdraw from the study will be treated without prejudice.

No study procedures will be performed nor IPs released to any subject who has not signed the assent or IC form or whose parent or legal guardian has not signed the IC form.

### **7.2 Medical History**

A complete medical history will be obtained at Screening (Visit 1).

### **7.3 Prior Medications and Concomitant Medications**

Investigator's need to be aware that patients often have severe pruritus and will be prescribed medications as well as take OTC medications to treat this condition. The PI needs to inform the subject of prohibited topical medications used for itching or other indication, including over-the-counter (OTC) cortisone products, as these may interfere with efficacy evaluations. Non-medicated lotions are allowed after IP is washed off (e.g., non-scented, hypoallergenic, etc.). Subjects will be instructed not to take any oral prescription medications without prior consultation with the Investigator unless their primary physician otherwise instructs. Oral Benadryl® (diphenhydramine) and other oral OTC anti-pruritics are allowed for itch relief. Subjects will be instructed to tell their primary physician of their participation in this study if they consult their physician during the study. Any therapy taken by the subject in the 4 weeks before randomization (Visit 1) will be reported as prior medication. Any therapy started or

stopped by the subject during the study after randomization will be regarded as concomitant therapy.

All prior and concomitant medications including topical treatments (prescription and over the counter, vitamins, and mineral supplements, and/or herbs) will be documented and must include the following information:

- Medication name
- Indication
- Start date
- Stop date or “Ongoing”

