## PROTOCOL SYNOPSIS

|  |                               |
|--|-------------------------------|
| TITLE:
A Phase 3, Randomized, Double Blind, Placebo-Controlled Study to Assess the Safety and Efficacy of Natroba™ (spinosad) for the Treatment of Scabies   |                               |
| PROTOCOL NUMBER:
SPN-304-15  |                               |
| INVESTIGATIONAL PRODUCT:
Natroba™ (spinosad) Topical Suspension, 0.9%  | U.S. IND No.
66,657 |
| PHASE:
3   |                               |
| INDICATION:
Treatment of scabies   |                               |
| OBJECTIVES:
The primary objective is to assess the safety and efficacy of topical Natroba™ (spinosad) versus Placebo for the complete cure of scabies after a single treatment.  |                               |
| ENDPOINTS:
The primary efficacy endpoint is the proportion of “index” subjects completely cured of scabies by Day 28. The “index” subject is defined as the youngest infested household member (≥4 years). Complete cure is defined as demonstration of both clinical cure (all signs and symptoms have completely resolved, including burrows, inflammatory/non-inflammatory lesions and pruritus) and microscopic or dermatoscopic cure demonstrating the absence of mites, eggs, and/or scybala, and negative dermatoscopy for burrows.

Safety endpoints include the evaluation of adverse events, general skin and eye irritation, clinical laboratory assessments, vital signs, and use of prior and concomitant medications.  |                               |
| POPULATION:
Approximately 360 subjects will be enrolled in the study. The approximate 360 total is based on: 120 households, each with an “index” subject and approximately 2 additional subjects per household (infested or not) for 360 total. The 120 “index” subjects with confirmed scabies infestation will comprise the primary efficacy population in order to achieve, with attrition, 48 subjects completed per treatment group (Natroba™ versus Placebo). In this study, “index” subjects will be defined as the youngest infested household member (≥4 years). All household members of the “index” subject will be randomized to the same treatment.  |                               |

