**Prior/concomitant medications**

Partial start dates of the concomitant medications will be assumed to be the earliest possible date consistent with the partial date. Partial stop dates of prior and concomitant medications will be assumed to be the latest possible date consistent with the partial date. In the case of the completely missing stop date, medication will be assumed to be ongoing.

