#### **6.4.5. Prior and Concomitant Medications**

The number and percent of subjects who took prior medications will be summarized descriptively by the Anatomical Therapeutic Chemistry (ATC) class and Preferred Term as coded in the WHO-Drug dictionary (WHO-DD) for each treatment group. Prior medications include all medications that start prior to first dose of study medication. Concomitant medications will be summarized similarly.

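### Protocol 7.3 leaves a drug taken continuously from before Day 1 through Day 28 out of the concomitant-medication summary, so on-study use is understated and can differ spuriously between arms

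*Protocol*

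**What the plan says.** Protocol 7.3 sets up two classes. For prior medication: "Any therapy taken by the subject in the 4 weeks before randomization (Visit 1) will be reported as prior medication". For concomitant therapy, the drug must have been started or "stopped by the subject during the study after randomization will be regarded as concomitant therapy". There is no clause for a therapy that simply runs on.

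SAP 6.4.5 draws the line for prior medication elsewhere: "Prior medications include all medications that start prior to first dose of study medication". On the other class it says only: "Concomitant medications will be summarized similarly". Protocol 8.5.4 gives the same instruction and no definition. The SAP's partial-date rules (6.1.3) add: "In the case of the completely missing stop date, medication will be assumed to be ongoing".

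The Protocol Synopsis lists among the safety endpoints "vital signs, and use of prior and concomitant medications". On itch, Protocol 7.3 warns that "patients often have severe pruritus and will be prescribed medications as well as take OTC medications to treat this condition". It bars topical anti-itch products, but oral diphenhydramine "and other oral OTC anti-pruritics are allowed for itch relief". Protocol 8.5.3.1 makes resolution of pruritus a condition of complete cure.

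**The concern.** A therapy already running on Day 1 and still running on Day 28 was neither started nor stopped after randomization. Under the only written definition it is not concomitant, although it was taken on every day of the study.

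For itch treatment the omission is tied to response. A subject whose itch persists and who keeps taking an oral antipruritic is left out; a subject whose itch clears and who stops is counted. If stopping differs by arm, so does the misclassification.

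Two things are at stake. Concomitant medication use is a named safety endpoint. And a reader who asks whether antipruritics influenced the Day 28 pruritus judgement needs on-study use by arm. The prior-medication table cannot supply it, because it mixes drugs stopped before Day 1 with drugs taken to the end.

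**Working it through.** **Step 1: apply the definitions case by case.**

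| Pattern of use | Protocol 7.3 | SAP 6.4.5 | Taken on study? |
|---|---|---|---|
| Stopped in the 4 weeks before Day 1 | prior | prior | no |
| Begun before Day 1, stopped during the study | prior and concomitant | prior; concomitant undefined | yes |
| Begun before Day 1, still taken at Day 28 | prior only | prior; concomitant undefined | yes |
| Begun after first dose | concomitant | not prior; concomitant undefined | yes |

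The third row is the gap. A drug with a completely missing stop date is treated as ongoing, so if begun before Day 1 it falls there too. One example needs no assumed rate: inclusion criterion 7 requires systemic contraceptives to have been in use for at least 3 months, so a subject who continues one unchanged is not counted as taking it concomitantly.

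The boundaries also differ. The protocol uses randomization with a 4-week look-back; the SAP uses first dose with no look-back limit.

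**Step 2: inputs for an illustration.** The plan gives no figure for antipruritic use, so there is none to reproduce. From Protocol 8.1:
- Index subjects per arm: 48/(1 − 0.20) = 60.
- Cure rates: 60% Natroba, 30% placebo. The sample-size row carrying them (48 per arm, Fisher's exact test, stated power 80.0%) recomputes to 80.05%.

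Assumptions, not in the documents:
- q = share on an oral antipruritic on Day 1, equal in both arms.
- c = share of those who stop before Day 28, set equal to the cure rates (cN = 0.60, cP = 0.30).
- s = share of non-users who start one after randomization (sN, sP).

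**Step 3: formulas.**
- Concomitant under 7.3 = q·c + (1 − q)·s
- Actual on-study use = q + (1 − q)·s
- Omitted = q·(1 − c), which is the baseline users still on the drug at Day 28
- Distortion of the Natroba-minus-placebo difference = q·(cN − cP) = 0.30q

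**Step 4: base case.** With q = 60%, 36 of 60 per arm are users on Day 1, and nobody starts later.
- Natroba: 0.60 × 36 = 21.6 stop, 21.6/60 = 36% counted; 14.4/60 = 24% omitted.
- Placebo: 0.30 × 36 = 10.8 stop, 10.8/60 = 18% counted; 25.2/60 = 42% omitted.
- Actual on-study use: 36/60 = 60% in each arm.

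**Step 5: range (Natroba vs placebo).**

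| q | New starters | Table under 7.3 | Actual on-study use |
|---|---|---|---|
| 60% | 0% / 0% | 36% vs 18% | 60% vs 60% |
| 50% | 0% / 0% | 30% vs 15% | 50% vs 50% |
| 50% | 5% / 10% | 32.5% vs 20.0% | 52.5% vs 55.0% |
| 30% | 0% / 0% | 18% vs 9% | 30% vs 30% |
| 30% | 5% / 10% | 21.5% vs 16.0% | 33.5% vs 37.0% |
| 30% | 5% / 20% | 21.5% vs 23.0% | 33.5% vs 44.0% |

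The table shows more use on Natroba only while sP − sN is below 0.30q/(1 − q): 7.5 points at q = 20%, 12.9 at 30%, 30 at 50% and 70 at 70%. In the last row the sign is right, but a 10.5-point gap shrinks to 1.5.

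**Step 6: denominator.** Safety summaries use about 360 subjects (SAP 5.1), roughly 180 per arm. If only index subjects contributed users, the base case would read 21.6/180 = 12% vs 10.8/180 = 6%, against actual use of 36/180 = 20% in each arm. Other infested household members would change this by an unknown amount.

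**The case against.** The best defence is that this is a labelling matter. The drug is not lost: it is in the prior-medication table, and the listings carry its start date and ongoing status. That stands, so a reader who infers that such drugs go uncounted altogether goes too far; they are missing from the concomitant summary only.

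Other text also points to a wider working meaning. The Day 14 call asks whether concomitant medications were used, Protocol 6.1 lists them at Visit 1, SAP 6.1.3 imputes dates in order to place events in study periods, and SAP 6.4.5 does not say that a prior drug cannot also be concomitant. A programmer might well classify by overlap with the treatment period. But none of these places states that rule, and applying it would depart from the only written definition.

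A reader might also infer that the table reverses the true picture, by setting 36% vs 18% beside the 24% vs 42% still on treatment at Day 28. Those are different quantities: use at any time under the 7.3 rule, and use on one day. On the same assumptions a correctly defined table reads 60% vs 60%, so the error there is a spurious difference. The sign of any-time use can flip (30% baseline use, starters 5%/10%), but not if enough more placebo subjects start an antipruritic.

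Finally, Protocol 7.3 says that itch treatment is common. It does not say that such treatment usually begins before Day 1 and runs unbroken to Day 28, so how many subjects fall in the gap is unknown.

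**Conclusion.** The point holds as a definitional gap with a limited reach. As written, the concomitant summary omits every therapy that spans the whole study and so understates on-study use. Where stopping differs by arm it also distorts the comparison, by q·(cN − cP): 18 points in the base case, 9 points at 30% baseline use. These sizes rest on assumed antipruritic use, on stopping rates borrowed from the planned cure rates, and on the index subjects as denominator.

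The documents do not support reading this as a threat to the primary result. The medication summaries are descriptive, and neither the CMH test, the imputation rules nor the sample size uses the label. The per-protocol exclusions turn on actual use of a scabicide or medicated lotion. What suffers is one safety table and the ability to interpret the pruritus component of cure.

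**What to change.** - In Protocol 7.3 and SAP 6.4.5, define concomitant as any therapy taken on or after the first dose of IP, whatever its start date: stop date on or after first dose, missing, or recorded as ongoing.
- State that a drug spanning the first dose appears in both the prior and the concomitant summaries, and use first dose as the boundary in both documents.
- Add a table, by arm in the I-ITT population, of antipruritics in use on the date of the Day 28 visit, derived from the recorded start and stop dates. The new definition alone would not show this, because it counts use at any time. Subjects without a Day 28 visit should be shown separately.

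The cost is about one sentence in each document and one extra table. Drug name, indication, start date, and stop date or ongoing status are already collected under Protocol 7.3, so no new data are needed. The SAP text should be settled before unblinding.

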#### **7.4 Prohibited Medications**

Subjects should not use any scabicide within 4 weeks before Visit 1, or use any scabicide, or rescue Permethrin, prescription or OTC medicated lotions, other than the IP during the study, through Day 28. There will be no washout of prohibited medications, subjects will be excluded or withdrawn from the study for use of prohibited medications.

#### **7.5 Pregnancy and Contraceptive Use**

Urine pregnancy tests will be conducted on women of childbearing potential at screening (Visit 1) and end of study (Visit 3/ET). Such subjects should be willing and able to practice an acceptable method of contraception during the study. Examples of acceptable contraceptive methods include abstinence, intrauterine device (IUD), double barrier method, oral or implantable or injectable contraceptives. Must have been using systemic (oral, injectable, or implantable) contraceptives for at least 3 months. If abstinence is their primary method of birth control they should be instructed to use a double barrier method if they become sexually active with another household member.

#### **7.6 Scabies Assessment**

Skin will be examined at Visits 1 and 3/ET to establish positive or negative evidence of active scabies infestation.

- Scabies diagnosis – active scabies infestation confirmed by clinical signs and symptoms (evidence of burrows or presence of scabies inflammatory/non-inflammatory lesions and pruritus) as well as by microscopic examination of skin scraping or dermatoscopy to demonstrate the presence of mites, eggs, and/or scybala. If dermatoscopy is used it should also confirm there are burrows on the skin.

- Primary Efficacy Endpoint – complete cure is defined as demonstration of clinical cure (all signs and symptoms have completely resolved, including burrows, inflammatory/non-inflammatory lesions and pruritus) and microscopic or dermatoscopic cure with demonstration of the absence of mites, eggs, and/or scybala, and dermatoscopy negative for burrows.

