### 3 INVESTIGATIONAL PLAN

#### 3.1 Overall Study Design

The study is a double blind, two-arm, 28-day, placebo-controlled study randomizing approximately 120 infested “index” subjects 1:1 to Natroba™ or Placebo in order to have at least 96 subjects completed (Figure 3-1).

Figure 3-1: FLOW DIAGRAM

All members of a household (no more than 6 individuals) with a suspected “index” subject must be screened at the first visit. In this study, “index” subjects are defined as the youngest infested household member ( $\geq 4$  years). If the household has at least one member with active scabies infestation and meet all other criteria, they must all agree to participate in the study. Household members who do not present with scabies at the screening visit must also agree to apply the same blinded investigational product (IP) as household members who present with scabies (see Table 6-1 Schedule of Procedures for status assessment). All household members must agree to participate in the study or none will be enrolled. Screening procedures include informed consent, medication and medical history, urine pregnancy test for females of childbearing potential, scabies assessment (visual evidence of burrows, inflammatory/non-inflammatory lesions and pruritus), microscopic examination of skin scraping or dermoscopy to demonstrate the presence of mites, eggs, and/or scybala (dermatoscopy must confirm burrows), vital signs, general skin and eye assessment, randomization, and IP dispensing and instruction.

After screening on Day 1, all randomized subjects will be dispensed IP (Natroba™ or Placebo) to apply at home later the same day as a single treatment over the entire body from the neck down to the toes (including the soles of the feet) and to the scalp (if balding) or hairline, temples and forehead on the same day. Subjects less than 12 years of age should be assisted with administration by a parent, guardian or caregiver. Subjects will rub the treatment into the skin followed by a 10-minute wait period before getting dressed. Showering or bathing must not occur earlier than 6 hours after treatment and no later than at least 1 hour prior to Day 2 visit.

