On Day 2 (Visit 2), all household members will return for general skin and eye assessments of possible irritation, and to confirm that all IP was left on for a minimum of 6 hours before bathing or showering. If a subject reports an adverse event assessed as related by the PI on Day 2 (Visit 2) then a follow-up visit with the investigator must be scheduled within 7 days of visit. All household members will receive a well-being phone call on Day 14 to continue to emphasize instructions to prevent re-infestation, determine if any concomitant medications have been used, and check for adverse events. If a subject reports an adverse event assessed as related by the PI on the Day 14 well-being phone call, then a follow-up visit with the investigator must be scheduled within 7 days of phone call.

On Day 28 (Visit 3), all household members will return to the clinic for safety and efficacy assessments. The primary endpoint of complete cure as well as the key secondary endpoint to determine improvement based on lesion count will be assessed in the “index” subject and any infested household members. If the infested subject is completely cured at Day 28, he or she will have completed the study and termination procedures will be conducted. If the subject is not completely cured at Day 28 (with Natroba™ or Placebo), the subject will receive 5% Permethrin and will be directed to their primary care physician for follow-up.

Safety assessments will be made for all household members and will include monitoring of adverse events (AEs) throughout the study, vital signs recording (Days 1 and 28), and general skin and eye irritation assessments (Days 1, 2, and 28).

The Day 28 procedures will also be completed for early termination (ET) except subjects will not receive rescue Permethrin but will be directed to follow-up with their primary care physician.

The trial design is presented in the Study Flow Diagram (Figure 3-1) and the visit assessments are described in the Schedule of Procedures (Table 6-1).

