| Weigh and dispense IP bottle;
provide application instructions    | X                                |                     |                 |                     |                     |                     |
| Instruct on waiting ≥6 hrs post-
treatment (IP) before showering  | X  |                     |                 |                     |                     |                     |
| Collect and weigh used IP bottle   |  | X                   |                 |                     |                     |                     |
| Review subject compliance    |  | X                   |                 |                     |                     | X       |
| Instructions to prevent re-
infestation                                       | X  | X                   |                 | X                   |                     |                     |
| Concomitant medications  |  | X                   |                 | X                   |                     | X                   |
| Adverse events   |  | X                   | X  | X                   | X      | X                   |
| 5% Permethrin dispensed to
subjects not completely cured at
Day 28         |  |                     |                 |                     |                     | X      |

ET = Early Termination; IP = investigational product.

1. Only for females of childbearing potential.
2. Scabies diagnosis (Inclusion #2) – At least one household member with active scabies infestation confirmed by clinical signs and symptoms (evidence of burrows or presence of scabies inflammatory/non-inflammatory lesions and pruritus) as well as by microscopic examination of skin scraping or dermatoscopy

to demonstrate the presence of mites, eggs, and/or scybala. If dermatoscopy is used it should also confirm there are burrows on the skin.

3. Primary Endpoint – Complete cure is defined as demonstration of clinical cure (all signs and symptoms have completely resolved, including inflammatory/non-inflammatory lesions and pruritus) and microscopic or dermatoscopic cure with demonstration of the absence of mites, eggs, and/or scybala, and dermatoscopy negative for burrows.
4. Vital signs – height (only Visit 1), weight, blood pressure (BP), and heart rate.

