### Number of New Lesions

The number of new lesions at Day 28 will be analyzed using a negative binomial regression model to compare the treatment difference. The model will include treatment group and study site (small sites pooled) as fixed factors, and baseline total lesion count as a covariate.

This analysis will be performed on the I-ITT population.

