### Total Lesion Counts

Total lesion counts will be calculated as the sum of pre-existing lesions and new lesions. The baseline captures the total lesions on the day of first study drug administration.

The change from baseline to Day 28 will be analyzed using an analysis of covariance (ANCOVA) model with treatment and study site (small sites pooled) as factors and baseline total lesion counts as a covariate.

This analysis will be performed on the I-ITT population.

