## **4. EFFICACY PARAMETERS**

### **4.1. Scabies Assessment**

Skin will be examined on Days 1 and 28/ET to establish positive or negative evidence of active scabies infestation.

- Scabies diagnosis – active scabies infestation confirmed by clinical signs and symptoms (evidence of burrows or presence of scabies)

inflammatory/non-inflammatory lesions and pruritus) as well as by microscopic exam of skin scraping or dermatoscopy to demonstrate the presence of mites, eggs, and/or scybala. If dermatoscopy is used it should also confirm there are burrows on the skin.

- Primary Efficacy Endpoint – complete cure is defined as demonstration of clinical cure (all signs and symptoms have completely resolved, including burrows, inflammatory/non-inflammatory lesions and pruritus) and microscopic or dermatoscopic cure with demonstration of the absence of mites, eggs, and/or scybala, and dermatoscopy negative for burrows.

Lesions should be indicated on a body diagram and/or marked with skin marker; count of existing and new lesions will be recorded.

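### SAP 4.1 accepts a skin marker as the only record of lesion position, so the exploratory count of new lesions at Day 28 may lack a durable Day 1 reference

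*Protocol*

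**What the plan says.** **Site procedures.** Protocol 7.6 opens with "Skin will be examined at Visits 1 and 3/ET to establish positive or negative evidence of active scabies infestation", followed by the diagnostic criteria and the definition of complete cure. In Table 6-1, the footnote to the Day 28 efficacy row begins "Complete cure is defined as demonstration of clinical cure" and goes no further than cure. Sections 6.1 and 6.6 list a scabies assessment and efficacy assessments without further detail. None of these places mentions a lesion count or a lesion map.

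**Recording rule.** The only instruction is in SAP 4.1, in a section covering Days 1 and 28/ET: "Lesions should be indicated on a body diagram and/or marked with skin marker; count of existing and new lesions will be recorded".

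**Analyses that use the data.** Protocol 3.1 says that a "key secondary endpoint to determine improvement based on lesion count will be assessed" at Day 28. Protocol 8.5.3.2 places the lesion analyses under exploratory efficacy. For new lesions: "The number of new lesions at Day 28 will be analyzed using a negative binomial regression model to compare the treatment difference", with the baseline total count as covariate. For total lesions, analysed by ANCOVA of change: "The baseline captures the total lesions on the day of first study drug administration". SAP 6.1.2 grades improvement by percent reduction in the total, and SAP 6.3.2 repeats both models.

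**Washing.** Protocol 3.1 requires a shower or bath at least 6 hours after application and "no later than at least 1 hour prior to Day 2 visit". Section 7.8 says the same.

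**The concern.** A lesion counts as new at Day 28 only by comparison with where lesions were on Day 1. SAP 4.1 allows that comparison to rest on skin marks alone. Those marks are followed by whole-body application of the product, a required wash within about a day, and roughly four weeks before the next scabies examination. If the marks are gone, the assessor has no positional reference, and the split between old and new becomes a judgement from memory or appearance. Day 1 positions cannot be recovered later.

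A second, smaller point is placement. The protocol's endpoints and models rely on the counts and on the old/new split, but the procedures that sites follow do not ask for either. A site reading only Protocol 7.6 and Table 6-1 would not learn that a map or a count is expected.

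**Working it through.** The plan states no figure on this point, and the documents give no sample-size assumption for the lesion endpoints. The check sets the passages side by side.

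**Step 1. What satisfies the recording rule.** SAP 4.1 joins diagram and marker with and/or. Three practices therefore comply: diagram only, marker only, or both. The requirement to record counts applies in all three.

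**Step 2. How long a marker-only record must last.** Marks are made on Day 1. Table 6-1 puts Visit 3 at Day 28 ± 2, that is Day 26 to Day 30. The marks must be legible for 26 − 1 = 25 to 30 − 1 = 29 days, unless the subject terminates early, and through the required wash before Visit 2. The Day 2 skin examination is for irritation and wash-off (Protocol 6.2). Nothing asks staff to renew marks there, and by then the subject has already washed. The documents do not say how long the marks last.

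**Step 3. Which endpoints need the old/new split.** Let E be the true number of pre-existing lesions still present at Day 28 and N the true number of new ones. Suppose a fraction a of the old lesions is called new, and a fraction b of the new lesions is called old.

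- Recorded new = N(1 − b) + aE
- Recorded pre-existing = E(1 − a) + bN
- Recorded total = E + N, whatever a and b are

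| Quantity | Needs | Affected by wrong old/new labels? |
|---|---|---|
| Complete cure (primary) | lesions, burrows and pruritus resolved; negative microscopy or dermatoscopy | No |
| Total lesions, change from baseline | count on Day 1 and at Day 28 | No, the errors cancel in the sum |
| Percent reduction, improvement grade | same two counts | No |
| Baseline covariate in both models | Day 1 count | No |
| New lesions at Day 28 | Day 1 positions | Yes |

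**Step 4. What the error does to the new-lesion analysis.** The recorded count contains aE. If treatment clears old lesions, E differs between arms, so the recorded contrast in new lesions partly reflects persisting old lesions. Blinding does not prevent this, because the contamination depends on E and not on the assessor knowing the arm. The site factor in the model does not remove it either, because it arises within a site. The documents give no values for a or b, so the size cannot be computed.

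**Step 5. Placement.** The protocol's procedural text (6.1, 6.6, 7.6, Table 6-1) contains neither count nor map. Its design narrative (3.1) and statistics section (8.5.3.2) presuppose a Day 1 total and an old/new split.

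**The case against.** The case on the other side has four parts.

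- **The counts are not missing from the plan.** Protocol 8.5.3.2 presupposes a Day 1 total, 3.1 says lesion-count improvement will be assessed, and 8.4 lists new and total lesions among the Day 28 data. SAP 4.1 says without condition that counts will be recorded. A version of the SAP is to be prepared when the protocol is finalised.
- **Other site documents are not in the file.** Protocol 11.1 has the eCRFs and their completion procedure reviewed with study staff at initiation. Count fields or a printed diagram may exist there.
- **Marker durability is not stated.** No passage says how long a mark lasts or whether it is refreshed.
- **The stakes are low.** The affected analysis is exploratory. The key secondary label appears only in the design narrative (Protocol 3.1, SAP 2.2). That labelling conflict is a separate matter and does not raise the weight of this point.

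All four stand, and they limit the point. They do not close it. The rule as written accepts a record that may not last, and no passage in either document requires one that does. An eCRF count field would not help with the split, because it holds a number and not positions.

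**Conclusion.** The point holds in a narrow form. A site that follows SAP 4.1 to the letter with a skin marker alone may have no usable Day 1 reference at Day 28, and the exploratory new-lesion analysis would then rest on unreliable labels. The primary endpoint, total count, change from baseline and improvement grade are not affected. The absence of the instruction from Protocol 7.6 and Table 6-1 is a gap of placement.

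A reader might infer more, but the documents do not support it:

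- **That no Day 1 count will exist, so all 120 or so index subjects are lost to the lesion analyses.** SAP 4.1 requires counts, and the eCRF content is unknown.
- **That each marker-only site drops out of these analyses.** Such a site still records counts. The harm is misclassification in one endpoint, not lost subjects.
- **That the required wash would certainly remove the marks.** That is an inference. The documents support only that marks may not survive.
- **That the multiple-imputation sensitivity analysis fails.** SAP 6.1.5 names a baseline lesion score without defining it, and lesion presence is already assessed at Visit 1.

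The conclusion assumes that at least one site uses a marker without a diagram, and that no unseen site document makes the diagram compulsory. This is a cheap improvement and not a threat to the trial's main result.

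**What to change.** - In Protocol 7.6, require that at Visit 1 the lesions of every infested subject are drawn on a body diagram and counted, and that at Visit 3/ET the same diagram is used to count pre-existing and new lesions separately.
- Add the count and diagram to Table 6-1 at both visits, as a row or a footnote.
- In SAP 4.1, remove the option of a marker alone. The diagram becomes mandatory and the skin marker an optional addition.

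The cost is one diagram and a few extra minutes per infested subject at two examinations already scheduled, an amendment line, and eCRF fields for the counts if they are not already there. No visit, treatment or eligibility rule changes.
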